3.0980	Full Safety	Mock-up SAFE_T7	Summary for Change from Baseline to Worst Post-Baseline in Schirmer's Test and Tear Break-up Time	See Section 8.5 Ocular findings from ophthalmic exam for details. Tear break-up time/Schirmer's test: increase in value means improvement.,	SAC [1] ,SAC [2]
3.1340	Full Safety	Mock-up SAFE_T9a	Shift in Schirmer's Test from Baseline to Worst Post-Baseline	See Section 8.5 Ocular findings from ophthalmic exam for details	SAC [1]
3.1350	Full Safety	Mock-up SAFE_T9a	Shift in Tear Break-up Time from Baseline to Worst Post-Baseline	See Section 8.5 Ocular findings from ophthalmic exam for details	SAC [1]
3.1000	Full Safety	Mock-up SAFE_T9	Shift in Slit Lamp Exam Findings from Baseline to Worst Post-Baseline	By eye (R/L) and subject (worse eye). See Section 8.5 Ocular findings from ophthalmic exam for details.	SAC [1] ,SAC [2]

Safety: Tables					
No.	Population	IDSL / Example Shell	Title	Programming Notes	Deliverable [Priority]
3.1010	Full Safety	Mock-up SAFE_T12	Summary of Presence of Iris Findings at Any Time Post-Baseline	By eye (R/L) and subject (either eye). Summary tables for number (%) of eyes with 'Transillumination defect', 'Nodules', or 'Neovascularization' at any post-baseline ocular exam. See Section 8.5 Ocular findings from ophthalmic exam for details.	SAC [1] ,SAC [2]
3.1020	Full Safety	Mock-up SAFE_T9	Shift in Pseudophakia and Cataracts from Baseline to Worst Post-Baseline	By eye (R/L) and subject (worse eye). See Section 8.5 Ocular findings from ophthalmic exam for details.	SAC [1]
3.1040	Full Safety	Mock-up SAFE_T8	Number of Subjects (%) Underwent Surgery due to Cataract Post-Baseline		SAC [1]
3.1050	Full Safety	Mock-up SAFE_T9	Shift in Findings from FUNDUS Photograph from Baseline to Worst Post-Baseline	By eye (R/L) and subject (worse eye). See Section 8.5 Ocular findings from ophthalmic exam for details.	SAC [1]
Ocular findings for General study from EOT to last follow-up visit					
3.1060	Full Safety	Mock-up SAFE_T15	Summary of Change (Worsening, No Change, Improvement) in Best Corrected Visual Acuity (BCVA) from EOT Visit to Last Follow-Up Visit	By eye (R/L) and subject (worse eye).	SAC [1] ,SAC [2]
3.1070	Full Safety	Mock-up SAFE_T15	Summary of Change (Worsening, No Change, Improvement) in Intraocular Pressure (IOP) from EOT Visit to Last Follow-Up Visit	By eye (R/L) and subject (worse eye). For IOP, decrease in value means improvement.	SAC [1]
3.1080	Full Safety	Mock-up SAFE_T15	Summary of Change (Worsening, No Change, Improvement) in Corneal Epithelium Findings from EOT Visit to Last Follow-Up Visit	By eye (R/L) and subject (worse eye). See Section 8.5 Ocular findings from ophthalmic exam for details	SAC [1] ,SAC [2]
3.1090	Full Safety	Mock-up SAFE_T15	Summary of Change (Worsening, No Change, Improvement) in Corneal Endothelium Findings from EOT Visit to Last Follow-Up Visit	By eye (R/L) and subject (worse eye). See Section 8.5 Ocular findings from ophthalmic exam for details	SAC [1] ,SAC [2]

Safety: Tables					
No.	Population	IDSL / Example Shell	Title	Programming Notes	Deliverable [Priority]
3.1100	Full Safety	Mock-up SAFE_T15	Summary of Change (Worsening, No Change, Improvement) in Pachymetry, Tear break up time, and Schirmer's test from EOT Visit to Last Follow-Up Visit	By eye (R/L) and subject (worse eye). Pachymetry: decrease in value means improvement; Tear break-up time/Schirmer's test: increase in value means improvement.,	SAC [1]
3.1110	Full Safety	Mock-up SAFE_T4	Summary of Resolution Time from EOT Visit in Best Corrected Visual Acuity (BCVA)	By eye (R/L) and subject (worse eye).	SAC [1] ,SAC [2]
3.1120	Full Safety	Mock-up SAFE_T4	Summary of Resolution Time from EOT Visit in Intraocular Pressure (IOP)	By eye (R/L) and subject (worse eye).	SAC [1]
3.1130	Full Safety	Mock-up SAFE_T4	Summary of Resolution Time from EOT Visit in Corneal Epithelium Findings	By eye (R/L) and subject (worse eye). See Section 8.5 Ocular findings from ophthalmic exam for details	SAC [1] ,SAC [2]
3.1140	Full Safety	Mock-up SAFE_T4	Summary of Resolution Time from EOT Visit in Corneal Endothelium Findings	By eye (R/L) and subject (worse eye). See Section 8.5 Ocular findings from ophthalmic exam for details	SAC [1] ,SAC [2]
3.1150	Full Safety	Mock-up SAFE_T4	Summary of Resolution Time from EOT Visit in Pachymetry, Tear break up time, and Schirmer's test	By eye (R/L) and subject (worse eye).	SAC [1]
Ocular sub-study (Cycle 1- 4)					
3.1160	Ocular Sub-Study	Mock-up SAFE_T16	Summary of Worst Grade of Corneal Events (GSK Scale) during Cycle 1-4 by Randomized Topical Corticosteroids Treatment		SAC [1]
3.1170	Ocular Sub-Study	Mock-up SAFE_T17	Summary of Best Corrected Visual Acuity (BCVA) Scores (logMAR score) by Randomized Topical Corticosteroids Treatment		SAC [1]
3.1180	Ocular Sub-Study	Mock-up SAFE_T18	Summary of Onset Time to First Drug-Related Corneal Event (GSK Scale) by Randomized Topical Corticosteroids Treatment		SAC [1]

Safety: Tables					
No.	Population	IDSL / Example Shell	Title	Programming Notes	Deliverable [Priority]
3.1190	Ocular Sub-Study	Mock-up SAFE_T19	Summary of Onset Time to Initiation of Topical Corticosteroids Treatment in Eyes Not-Randomized to Topical Corticosteroids Treatment		Headline, SAC [1]
3.1200	Ocular Sub-Study	Mock-up SAFE_T20	Shift in Corneal findings (per Ocular Exam) from Baseline to Worst during Cycle 1-4 by Randomized Topical Corticosteroids Treatment		SAC [1]

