4. ANALYSIS POPULATIONS

Population		Definition / Criteria	Analyses Evaluated
All Screened		
 • All participants who sign the ICF to participate in the study. 	
 • Study Population
Enrolled		
 • All participants who passed screening. Note screening failures (who never passed screening even if rescreened) and participants screened but never enrolled into the study (Reserve, Not Used) are excluded from the Enrolled population as they did not enter the study. Same participant enrolled more than once will be counted only once based on the last randomization number. • This population will be based on the treatment the participant was randomized to. 	
 • Study Population
Frozen liquid configuration	Intent-to-Treat (ITT)	
 • All randomized participants whether or not randomized treatment was administered. • This population will be based on the treatment the participant was randomized to. • Any participant who receives a treatment randomization number will be considered to have been randomized. Same participant receiving multiple randomization numbers will be counted only once using the last randomization number. 	
 • Study Population • Efficacy • EORTC QLQ-C30 and EORTC QLQ-MY20
	Efficacy	
 • Efficacy population will consist of first 130 ITT participants whether or not randomized treatment was administered. This population will be based on the treatment to which the participant was randomized and will be used for sensitivity analysis of 	
 • Selected efficacy

Population		Definition / Criteria	Analyses Evaluated
		primary and selected secondary efficacy endpoints.	
	Evaluable	
 All participants who have at least two doses of study treatment and have completed at least one disease assessment after the second dose, or progressed or died or discontinued treatment due to other reasons. 	
 Futility analyses at IA
	Safety	
 All randomized participants who received at least one dose of Frozen liquid study treatment. This population will be based on the treatment the subject actually received (first dose). 	
 Safety PRO-CTCAE, NEI-VFQ-25 and OSDI.

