	Ocular Sub-Study	
 All randomized participants to ocular sub-study who received at least one dose of study treatment. This population will be used to evaluate the effect of topical corticosteroids on corneal events/findings in approximately 30 participants who will receive monocular topical corticosteroids for the first 4 cycles 	
 Corneal events/findings
Lyophilized configuration	Lyo	
 All randomized participants who receive at least 1 dose of lyophilized study treatment. 	
 All analysis other than PK
Full Analysis		
 All participants included in either ITT or Lyo population This population will be based on the treatment the participant was randomized to 	
 Study population Efficacy EORTC QLQ-C30 and EORTC QLQ-MY20
Full Safety		
 All participants who receive at least 1 dose of study treatment (frozen liquid or lyophilized). This population will be based on the treatment the subject actually received (first dose). 	
 Safety PRO-CTCAE, NEI-VFQ-25 and OSDI.
Full Pharmacokinetic (PK)		
 All participants in the Full Safety population who had at least 1 non-missing PK assessment (Non-quantifiable [NQ] values will be considered as non-missing values). 	
 PK

Note: Refer to [Appendix 13: List of Data Displays](#) which details the population used for each display being generated in the final version of the RAP.

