6.2. Disposition of Subjects

A summary of the number of subjects in each of the analysis populations described in Section 4 will be provided (for primary analysis, Evaluable population will not be included). In addition, the number of subjects enrolled by centre will be summarized by dose level using the “Enrolled” population. A separate summary for exclusions from each study population will be displayed (for primary analysis, Evaluable population will not be included). A listing of subjects excluded from analysis populations will also be provided.

A summary of subject status and reason for study withdrawal will be provided. This display will show the number and percentage of subjects who withdrew from the study, including primary reasons for study withdrawal. Reasons for study withdrawal will be presented in the order they are displayed in the eCRF.

A summary of study treatment status will be provided. This display will show the number and percentage of subjects who are ongoing or discontinued study treatment and a summary of the primary reasons for discontinuation of study treatment. Reasons for study treatment discontinuation will be presented in the order they are displayed in the eCRF. A listing of study treatment discontinuation will be generated. The listing will include last dose date, and reasons for study treatment discontinuation.

A listing of subjects with visits and assessments Impacted by the COVID-19 Pandemic will be presented. A stacked bar chart depicting visits impacted by COVID-19 will be presented.

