8.2.2. Eye disorder (CTCAE)

For AE in eye disorder SOC (CTCAE), an overview table and the listing will be provided.

In addition, for each of selected five types of event within eye disorder SOC (keratopathy, dry eye, blurred vision, photophobia, and eye pain), the following summary tables will be provided if the incidence rate $\geq 10\%$ is observed in 3.4mg/kg frozen liquid cohort

1. Event overview
2. Summary table by PT and Maximum Grade
3. Summary of event characteristics
4. Summary of time to onset, duration, and outcome
5. Summary of cumulative incidence by PT and number of doses received at first occurrence
6. Summary of percentage of time on study treatment with ongoing event

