3.0580	Full Safety	AE3	Summary of Serious Adverse Events by Preferred Term		Headline, SAC [1], SAC [2]
3.0130	Full Safety	AE3	Summary of Adverse Events Leading to Permanent Discontinuation of Study Treatment by Preferred Term		IA [1], Headline, SAC [1] , SAC [2]
3.0140	Full Safety	AE3	Summary of All Serious Drug-Related Adverse Events by Preferred Term		SAC [1] , SAC [2]
3.0150	Full Safety	AE3	Summary of Adverse Events Leading to Dose Reduction by Preferred Term		Headline, SAC [1] , SAC [2]

CONFIDENTIAL

205678

Safety: Tables					
No.	Population	IDSL / Example Shell	Title	Programming Notes	Deliverable [Priority]
3.0160	Full Safety	AE3	Summary of Adverse Events Leading to Dose Delays by Preferred Term		Headline, SAC [1], SAC [2]
3.0830	Full Safety	AE6	Summary of Cumulative Incidence of Serious Adverse Events by PT and Number of Doses Received at First Occurrence	Only PT term, no SOC needed. The number of doses received at first occurrence will be <= 1, <= 2, <= 4, <= 6, <= 8, <= 10, and Any	SAC [1], SAC [2]
AEs of Special Interest					
3.0170	Full Safety	OAE07	Summary of Keratopathy Events (CTCAE) by Preferred Term and Maximum Grade	Table need to be created only if the observed incidence rate >= 10% in 3.4 mg/kg Frozen liquid cohort.	SAC [1], SAC [2]
3.0171	Evaluable	OAE07	Summary of Dry Eye Events (CTCAE) by Preferred Term and Maximum Grade (Evaluable)	Table need to be created only if the observed incidence rate >= 10% in 3.4 mg/kg Frozen liquid cohort.	SAC [1], SAC [2]
3.0172	Full Safety	OAE07	Summary of Blurred Vision Event (CTCAE) by Preferred Term and Maximum Grade	Table need to be created only if the observed incidence rate >= 10% in 3.4 mg/kg Frozen liquid cohort.	SAC [1], SAC [2]
3.0173	Full Safety	OAE07	Summary of Photophobia Event (CTCAE) by Preferred Term and Maximum Grade	Table need to be created only if the observed incidence rate >= 10% in 3.4 mg/kg Frozen liquid cohort.	SAC [1]
3.0174	Full Safety	OAE07	Summary of Eye Pain Event (CTCAE) by Preferred Term and Maximum Grade	Table need to be created only if the observed incidence rate >= 10% in 3.4 mg/kg Frozen liquid cohort.	SAC [1]
3.0180	Full Safety	ESI1	Summary of Characteristics of Keratopathy Events (CTCAE)	Table need to be created only if the observed incidence rate >= 10% in 3.4 mg/kg Frozen liquid cohort. Include summary of outcome of AE.	SAC [1], SAC [2]

CONFIDENTIAL

205678

Safety: Tables					
No.	Population	IDSL / Example Shell	Title	Programming Notes	Deliverable [Priority]

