3.0252	Full Safety	AE13	Overview of Dry Eye Event (CTCAE)	Table need to be created only if the observed incidence rate \geq 10% in 3.4 mg/kg Frozen liquid cohort. Same categories as AE overview	SAC [1] , , SAC [2]
3.0253	Full Safety	AE13	Overview of Blurred Vision Event (CTCAE)	Table need to be created only if the observed incidence rate \geq 10% in 3.4 mg/kg Frozen liquid cohort. Same categories as AE overview	SAC [1] , SAC [2]
3.0250	Full Safety	AE13	Overview of Photophobia Event (CTCAE)	Table need to be created only if the observed incidence rate \geq 10% in 3.4 mg/kg Frozen liquid cohort. Same categories as AE overview	SAC [1]
3.0250	Full Safety	AE13	Overview of Eye Pain Event (CTCAE)	Table need to be created only if the observed incidence rate \geq 10% in 3.4 mg/kg Frozen liquid cohort. Same categories as AE overview	SAC [1]
3.1320	Full Safety	Mock-up SAFE_T22	Summary of Percentage of Duration of Exposure with Keratopathy Events (CTCAE)	Table need to be created only if the observed incidence rate \geq 10% in 3.4 mg/kg Frozen liquid cohort.	SAC [1], SAC [2]

CONFIDENTIAL

205678

Safety: Tables					
No.	Population	IDSL / Example Shell	Title	Programming Notes	Deliverable [Priority]
3.1321	Full Safety	Mock-up SAFE_T22	Summary of Percentage of Duration of Exposure with Dry Eye Events (CTCAE)	Table need to be created only if the observed incidence rate >= 10% in 3.4 mg/kg Frozen liquid cohort.	SAC [1], SAC [2]
3.1322	Full Safety	Mock-up SAFE_T22	Summary of Percentage of Duration of Exposure with Blurred Vision Events (CTCAE)	Table need to be created only if the observed incidence rate >= 10% in 3.4 mg/kg Frozen liquid cohort.	SAC [1], SAC [2]
3.1323	Full Safety	Mock-up SAFE_T22	Summary of Percentage of Duration of Exposure with Photophobia Events (CTCAE)	Table need to be created only if the observed incidence rate >= 10% in 3.4 mg/kg Frozen liquid cohort.	SAC [1]
3.1324	Full Safety	Mock-up SAFE_T22	Summary of Percentage of Duration of Exposure with Eye Pain Events (CTCAE)	Table need to be created only if the observed incidence rate >= 10% in 3.4 mg/kg Frozen liquid cohort.	SAC [1]
3.0270	Full Safety	OAE07	Summary of Thrombocytopenia by Preferred Term and Maximum Grade		IA [1], SAC [1] , SAC [2]
3.0271	Evaluable	OAE07	Summary of Thrombocytopenia by Preferred Term and Maximum Grade (Evaluable)		IA [1]
3.0280	Full Safety	ESI1	Summary of Characteristics of Thrombocytopenia	Include summary outcome of AE;	IA [1], SAC [1] , SAC [2]

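### Table 3.0171, the dedicated dry-eye grade table, is assigned the interim Evaluable population at both final analyses instead of Full Safety

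*SAP*

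**What the plan says.** Section 8.2.2 promises a set of outputs for each of five eye events: keratopathy, dry eye, blurred vision, photophobia and eye pain. They are produced if the event reaches 10% incidence in the 3.4 mg/kg frozen liquid cohort. One of them is the "Summary table by PT and Maximum Grade".

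Section 15.13.8 turns that into Tables 3.0170 to 3.0174. The dry-eye member, 3.0171, is titled "Summary of Dry Eye Events (CTCAE) by Preferred Term and Maximum Grade (Evaluable"), has Evaluable in its population column, and is due at SAC [1] and SAC [2]. Section 15.13.3 defines these as the primary and end-of-study analyses. The keratopathy member, 3.0170 ("Summary of Keratopathy Events (CTCAE) by Preferred Term and Maximum Grade"), is due at the same two deliverables but on Full Safety.

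Section 4 lists Evaluable under the frozen liquid configuration, with the single use "Futility analyses at IA". Its definition begins "All participants who have at least two doses of study treatment and have completed at least one disease assessment after the second dose" and then also admits those who progressed, died or discontinued treatment for other reasons. Full Safety is "All participants who receive at least 1 dose of study treatment (frozen liquid or lyophilized"). The note under the Section 4 table points to Appendix 13 for the population of each display.

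**The concern.** Appendix 13 is where a programmer looks up the population, so the cell for Table 3.0171 decides what is produced. Followed literally, it puts one special-interest safety table on a population built for an interim efficacy decision. Membership depends on disease assessment, progression, death or discontinuation, rather than on having been dosed. It also contains no lyophilized participants.

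Dry-eye severity would then appear in its dedicated table without the lyophilized column and on a different denominator rule from keratopathy, blurred vision, photophobia and eye pain. The denominator would also go undocumented at the primary analysis, because Section 6.2 says of the population-count and exclusion summaries that "for primary analysis, Evaluable population will not be included".

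**Working it through.** No sample size, power or error rate is involved, so the check is a cross-reading of the display list against the population definitions.

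**1. The five grade tables promised in Section 8.2.2**

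| Table | Event | Population | Deliverable |
|---|---|---|---|
| 3.0170 | Keratopathy | Full Safety | SAC [1], SAC [2] |
| 3.0171 | Dry eye | Evaluable | SAC [1], SAC [2] |
| 3.0172 | Blurred vision | Full Safety | SAC [1], SAC [2] |
| 3.0173 | Photophobia | Full Safety | SAC [1] |
| 3.0174 | Eye pain | Full Safety | SAC [1] |

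Four of five use Full Safety. The exception is dry eye.

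**2. The other dry-eye displays from Section 8.2.2.** Tables 3.0181 (characteristics), 3.0201 (characteristics II), 3.0252 (overview), 3.0951 (cumulative incidence) and 3.1321 (percentage of exposure with the event) are all Full Safety.

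**3. Every display on Evaluable.** There are eleven: Tables 1.0121, 1.0161, 1.0301, 2.0030, 3.0011, 3.0041, 3.0171, 3.0271, 3.0301 and 3.0440, and Figure 3.0030. Ten are IA [1] only. Table 3.0171 is the only one scheduled for SAC [1] or SAC [2], and it has no IA deliverable at all.

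**4. Pairing.** The other Evaluable grade tables by preferred term each follow a Full Safety twin: 3.0040/3.0041, 3.0270/3.0271 and 3.0300/3.0301. For example, "Summary of Thrombocytopenia by Preferred Term and Maximum Grade (Evaluable") is 3.0271, produced at the interim only, beside Full Safety Table 3.0270. Table 3.0171 has no such twin.

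**5. Section 8.** Its opening paragraph names Safety, Full Analysis and, if needed, Lyo as the bases for safety analyses. Evaluable is not among them.

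**6. Where dry-eye grade can still be found in Full Safety**
- Table 3.0040 covers all adverse events by preferred term and maximum grade, at IA, Headline, SAC [1] and SAC [2]. It reports single preferred terms, not the dry-eye grouping.
- Table 3.0080 does the same for drug-related events, at SAC [1].
- Table 3.12961 gives dry eye by maximum grade, split by best response, at SAC [2] only.
- Table 3.0252 uses the adverse-event overview categories, which include Grade 3 and 4 events.
- Table 3.0181 probably shows maximum grade. It uses shell ESI1, and Section 8.2.1 describes that content for other events using the same shell. Table 3.12738 (ocular symptoms, SAC [2]) probably includes dry eye. Both are inferences from shell or title.

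**7. Who is left out.** All lyophilized participants are, by definition. Sections 2.2 and 2.3 plan about 25 of them against about 200 randomized to frozen liquid (Section 3.1.1.1), so roughly 25 / (200 + 25) = 11% of planned participants. In the frozen arms, those left out are dosed participants who meet none of the Evaluable conditions. The SAP does not allow that number to be computed.

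**The case against.** The best counter-argument is that this is a leftover label with little practical effect. Much of that stands. The pattern in the display list suggests a clerical slip, not a deliberate choice. The table is descriptive and conditional on 10% incidence, and it bears on no hypothesis or primary endpoint. It still needs correcting, because Appendix 13 fixes the population and the title carries the same error.

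Four stronger readings are tempting, and the SAP does not support them:

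- *Dry eye has no grade table in all treated participants.* It does: at least Tables 3.0040 and 3.12961 are Full Safety. What is missing is the dedicated table by preferred term and maximum grade.
- *The table would shrink to the interim size of about 25 per arm, with a matching loss of precision.* The Evaluable definition carries no data cut. Derived again six months after the last frozen-liquid randomization (Section 3.2), or later, it would take in most frozen-arm participants, since progression, death or discontinuation also qualifies. The SAP also plans no confidence intervals for these grade summaries.
- *The eye-toxicity tables could not be compared.* One display is affected. The other dry-eye tables share the Full Safety denominator with their keratopathy and blurred-vision counterparts, and Table 3.0040 allows comparison by preferred term with the lyophilized cohort included.
- *Section 6.2 abolishes Evaluable at the primary analysis.* It removes it only from the population-count and exclusion summaries.

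**Conclusion.** The population assigned to Table 3.0171 is wrong. It conflicts with the use Section 4 gives to Evaluable, with the safety bases in Section 8, with all four sibling tables, and with the interim-only pattern of the other ten Evaluable displays. As written, the SAP yields no dedicated dry-eye table by preferred term and maximum grade in Full Safety at either final deliverable.

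The certain cost is the lyophilized column, about 25 participants on the planned number, and a frozen-arm denominator defined differently from the sibling tables. How far the frozen-arm counts would differ cannot be read from the SAP. If Evaluable is derived afresh at the final data cuts, the difference is likely to be small. Because dry-eye grade remains available in other Full Safety displays, the severity is minor.

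**What to change.** In Section 15.13.8, change the population of Table 3.0171 from Evaluable to Full Safety and delete the word Evaluable from its title, so that it matches 3.0170 and 3.0172 to 3.0174. The cost is one cell and one title. No new data, shell or method is needed.

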15.13.9. Safety Figures

Safety: Figures					
No.	Population	IDSL / Example Shell	Title	Programming Notes	Deliverable [Priority]
Laboratory					
3.0020	Full Safety	LIVER14	Scatter Plot of Maximum vs. Baseline for ALT	IDSL	SAC [1]
3.0040	Full Safety	LIVER9	Scatter Plot of Maximum Bilirubin versus Maximum ALT – eDISH Plot	IDSL	SAC [1]
3.0050	Full Safety	LIVER9	Scatter Plot of Maximum AST vs Maximum LDH - eDISH Plot	IDSL	SAC [1]
3.0060	Full Safety	LIVER9	Scatter Plot of Maximum AST vs Maximum Creatinine Kinase - eDISH Plot	IDSL	SAC [1]
3.0070	Full Safety	LIVER9	Scatter Plot of Maximum LDH vs Maximum Creatinine Kinase - eDISH Plot	IDSL	SAC [1]
3.0080	Full Safety	LIVER9	Scatter Plot of Maximum Albumin/Creatinine Ratio (> 2000 mg/g) vs. Concomitant Values of Serum Creatinine	Concomitant window = \pm 7 days	SAC [1]
3.0090	Full Safety	EG8	Box Plot of Values for Selected Lab Tests by Visit	Selected lab tests are: haemoglobin, platelets, neutrophils, serum creatinine, and albumin/creatinine ratio.	SAC [1]
Profile Plot					
3.0030	Evaluable	Programming note	Profile Plot for Subjects (Evaluable)	See Figure 3.0030 created at IA for 205678	IA [1]
3.0031	Full Safety	Programming note	Profile Plot for Subjects	See Figure 12.0150 from BMA117159 (primary_01)	SAC [1]

Safety: Figures					
No.	Population	IDSL / Example Shell	Title	Programming Notes	Deliverable [Priority]
ECG					
3.0100	Full Safety	OECG4	Fridericia's QTc Shifts from Baseline to Worst-case Post Baseline		SAC [1]

CONFIDENTIAL

205678

Safety: Figures					
No.	Population	IDSL / Example Shell	Title	Programming Notes	Deliverable [Priority]
Corneal events					
3.10031	Full Safety	Programming note	Plot of Visual Acuity and Corneal Finding Grade for Subjects Experiencing >1 Corneal Event (GSK Scale), Initial Dose Level = 2.5 mg/kg	Refer present_2020_04	SAC [2]
3.53010	Full Safety	Programming note	Plot of Time to Recovery Post Treatment Discontinuation for Corneal Exam Findings	Refer regqry_2020_10	SAC [2]
3.53020	Full Safety	Programming note	Plot of Time to Recovery Post Treatment Discontinuation for Keratopathy	Refer regqry_2020_10	SAC [2]
3.50030	Full Safety	Programming note	Bar Chart of Grade of Corneal Exam Finding by Cycle	Refer regqry_2020_10	SAC [2]

